CLINICAL TRIAL PROTOCOL

Light and Ion Treatment to Enhance⁺ Medication Efficacy in Depression

(The LITE+MED Trial)

A Randomized Controlled Trial of Light Treatment and Fluoxetine in Patients with Nonseasonal Major Depressive Disorder

Principal Co-Investigators:

[name], University of British Columbia
[name]
[contact], [contact], [contact]

[name], University of Toronto

[name], University of Toronto

[name], University of BC

[name], University of Manitoba

[name], University of Toronto

[name], University of Toronto

[name], Sunnybrook Health Sciences Centre

[name], MDCM, McGill University

[name], Dalhousie University

[name], University of Calgary

[name], University of Calgary

Revised Version Date: November 18, 2010

CLINICAL TRIAL PROTOCOL

Light and Ion Treatment to Enhance+ Medication Efficacy in Depression.

A Randomized Controlled Trial of Light Treatment and Fluoxetine in Patients with Nonseasonal Major Depressive Disorder.

i. Table of Contents

A. Objectives	2
B. Overall Study Design	2
C. Outcome Measures	3
D. Study Population	5
E. Treatments	7
F. Procedures and Methods	8
G. Concomitant Therapy	9
H. Data Safety Monitoring Committee ...	10
I. Quality Assurance	10
J. Early Termination	11
K. Data Analysis	11
L. Informed Consent and Ethics	11
M. Publications and Communications	12
N. List of Investigators	12
O. References	12
P. Appendix: Summary of Procedures...13	

A. Study Objectives

The **primary objectives** of this study are to test the hypotheses that, in patients with nonseasonal major depressive disorder (MDD) of at least moderate severity: 1) light treatment with a fluorescent light box (10,000 lux white light for 30 minutes daily) is more effective than a placebo control condition, and 2) combined light treatment and antidepressant medication (fluoxetine) is more effective than placebo and both monotherapies.

The **secondary objectives** of this study are to investigate the effects of bright light treatment and fluoxetine on clinical response and remission rates, adverse events, quality of life, work productivity, and health services utilization.

[figure not shown]
B. Overall Study Design (see Figure 1)

This trial has been designed as a multicentre, double-blind, placebo-controlled, randomized, parallel-design study. A total of 216 patients meeting entry criteria will be enrolled at 6 centres over a 3 year period.

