Phase I is a one week baseline phase without treatment to quantify baseline pre-treatment measures (see Figure 1). In **Phase II**, subjects will be randomized to 1 of 4 treatment conditions for 8 weeks: 1) active light treatment using a fluorescent light box (10,000 lux white light for 30 minutes daily) plus a placebo pill, 2) placebo inactive negative ion generator (30 minutes daily) with fluoxetine 20 mg/d, 3) placebo inactive negative ion generator (30 minutes daily) plus placebo pill (double placebo), or 4) combined active light treatment using a fluorescent light box (10,000

lux white light for 30 minutes daily) plus fluoxetine 20 mg/d. Randomization will be conducted centrally via a web-based computerized system and stratified by sex and centre.

Figure 1. Protocol Summary (also see Appendix 1 – Summary of Procedures)

The primary measure of efficacy will be change score (baseline to termination) on the Montgomery-Asberg Depression Rating Scale (MADRS). Secondary measures of efficacy will include clinical response (50% or greater improvement in MADRS scores) and remission (final MADRS score of 10 or less), scores on the 24-item Hamilton Depression Rating Scale (Ham-24), the CGI, the Quick Inventory of Depressive Symptoms (QIDS-SR, Rush 2003), the Lam Employment Absence and Productivity Scale, and the Quality of Life, Enjoyment and Satisfaction Questionnaire. All of these outcome measures are widely used in depression research studies, are sensitive to change, and have been well validated (e.g., Lam et al, 2005). Safety and adverse events data will also be systematically recorded and compared across conditions. Utilization of health services data will be captured to estimate cost-effectiveness of each active treatment condition compared to placebo.

C. Outcome Measures (see Appendix 1)

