 5. The Adult ADHD Self-Report Scale (ASRS-v1.1) is a self-rated scale that assesses the severity of 18 symptoms associated with Attention Deficit/Hyperactive Disorder (ADHD) (Kessler et al., 2005). This scale is used as a screening tool for adults who exhibit symptoms of ADHD, and provides information to the clinician regarding the need for more in-depth clinical interview (Schweitzer et al., 2001; Barkley, 1998). The questions in the ASRS v1.1 are consistent with the DSM-IV criteria and manifestations of ADHD symptoms, and has high validity and reliability (Adler et al., 2006; American Psychiatric Association, 2000).
 6. Adverse Events Scale (CANMAT, 1999). Developed by the Canadian Network for Mood and Anxiety Treatment for use in the Emergency Drug Release program, this self-rated scale assesses both frequency and severity of 32 adverse events (including a category for “other”). This scale provides a more comprehensive and systematic evaluation of adverse events than is usually conducted in antidepressant clinical trials, and was used in the CIHR-funded CAN-SAD light treatment versus fluoxetine study (Lam et al, 2006).
 7. Lam Employment Absence and Productivity Scale (LEAPS, Lam, 2007). This 10-item self-report scale assesses absenteeism and presenteeism (work productivity) and has recently been validated in depressed patients.
 8. Quality of Life, Enjoyment and Satisfaction Questionnaire (Q-LES-Q, Endicott et al, 1993). The Q-LES-Q is a 16-item self-report questionnaire developed and validated for use in depressed outpatients. There are also single items that rate “overall life satisfaction and contentment” and “satisfaction with medications (if any are taken).” The Q-LES-Q has good test-retest reliability and is sensitive to change in clinical status.
 9. Pittsburgh Sleep Quality Index (PSQI) (Buysse et al., 1989). The PSQI is a subjective instrument used to assess the quality and pattern of sleep in adults. Patients score themselves on seven areas of sleep, including subjective sleep quality, sleep latency, sleep duration, habitual sleep efficiency, sleep disturbances, use of sleeping medication, and daytime dysfunction. The PSQI has good reliability and validity for use in adults across all health care settings (Buysse et al.).
 10. Fatigue Severity Scale (FSS, Krupp et al., 1989). This 9-item scale is designed to differentiate fatigue from clinical depression, as they exhibit similar symptoms. This scale is also a practical

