Participation will be voluntary. The nature of the study will be fully explained to the patient. The patient must have an educational level and degree of understanding such that he/she can communicate with the investigator and research staff intelligently. An informed consent document (ICD) will be signed by the patient and retained by the investigator. A signed copy will be given to both the patient and to the Study Coordinator. Patients should be reliable and must agree to keep appointments for clinic visits and all tests and examinations required by the protocol. All patients will be screened using the Mini International Neuropsychiatric Interview (MINI, Sheehan et al, 1998) to confirm the diagnosis and to rule out other primary illnesses (such as bipolar disorder, other depression/anxiety disorders, substance abuse, etc.). All patients will also be evaluated for risk of suicidality, using the Columbia Classification Algorithm of Suicide Assessment (C-CASA, Posner et al, 2007).

Inclusion Criteria

1. Male and female outpatients aged 19-60 years.
2. Patients will meet criteria for major depressive episodes as determined by a structured interview (Mini Neuropsychiatric Interview, MINI, Sheehan et al, 1998).

3. A score of 20 or greater on the clinician-rated Ham-17, indicating at least moderately severe depression, comparable to previous depression treatment studies.
4. Competency to give informed consent.

Exclusion Criteria

1. Pregnant women, lactating women and sexually active women of childbearing potential who are not using medically accepted means of contraception.
2. Serious suicidal risks as judged by the clinician, the MINI, the Ham-17, and the C-CASA.
3. The following DSM-IV diagnoses (to ensure a homogenous diagnostic group):
 - Major depressive disorder, recurrent, with a seasonal pattern
 - Organic mental disorders
 - Substance abuse/dependence, including alcohol, active within the last year
 - Schizophrenia, Paranoid or Delusional Disorders, or any other psychotic features
 - Obsessive-Compulsive Disorder, Post-Traumatic Stress Disorder
 - Panic disorder, Generalized Anxiety Disorder, if a primary diagnosis
 - Bipolar Disorder
 - Bulimia Nervosa; Anorexia Nervosa
4. Serious illness including cardiac, hepatic, renal, respiratory, endocrinologic, neurologic and hematologic disease that is not stabilized, or a past history of convulsions.

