5. Any retinal disease or systemic illness with active retinal involvement (e.g. diabetes) that precludes the use of bright light.
6. Patients who have a history of severe allergies and multiple drug adverse reactions.
7. Regular or current use of other psychotropic drugs including lithium and tryptophan.
8. Patients treated with beta blocking drugs.
9. Hypertensive patients being treated with guanethidine, reserpine, clonidine or methyldopa (because of possible mood-altering effects of those drugs).
10. Use of monoamine oxidase inhibitors within 14 days of Visit 1 (to ensure no drug interactions between fluoxetine and MAOIs), or use of heterocyclic antidepressant within 7 days of Visit 1 (to ensure adequate washout period of two weeks between stopping previous drug and start of treatment at Visit 2).
11. Previous use of fluoxetine or light therapy.
12. Treatment resistance in the current episode, as defined by failure (lack of clinically significant response) of two or more antidepressants given at therapeutic doses for at least 6 weeks.
13. Patients who started formal psychotherapy (e.g. cognitive-behavioural or interpersonal psychotherapy) within 3 months of Visit 1, or who plan to initiate such psychotherapy during this study.
14. Patients involved in any other form of treatment for depression.

Sample Size

Based on a power analysis using a minimal clinically important difference (MCID) and data derived from the largest and highest quality study of light and medication treatment for MDD (Martiny et al, 2005), we propose a sample size of 216 patients overall, or at least 54 randomized to each of the 4 groups with allowance for a 20% dropout rate (the average in our previous studies), recruited over 3 years. With regard to the primary hypothesis, this sample size will allow us to detect a difference of 3.5 points on the MADRS (widely regarded as a MCID in depression

treatment studies) between conditions with 80% power at two-sided testing at a Bonferroni-corrected $\alpha=0.017$ (3 planned comparisons: fluoxetine vs. placebo, light vs. placebo, light+fluoxetine vs. placebo).

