During the protocol, specific measures will be taken to maintain the blind for subjects. Subjects will be instructed not to talk about their treatment device. Subjects will not be scheduled for appointments at the clinic at the same time, so they will not be able to talk among themselves. Research personnel will minimize time with the subject and will not discuss the treatments with them.

Data Management

Data will be managed and analyzed by the Verity Strategy Group Inc. This group has extensive experience in managing large datasets and procedures in place to ensure integrity and

verification of data handling and analysis. They will design the web-Case Report Form (CRF) as a web-based dataform on a secure web site, for direct data entry by research staff.

J. Early Terminations

Every effort will be made to keep the subject in the study for the duration of the study. Acceptable reasons for premature discontinuation include the following:

1. Request of subject.
2. Decision of the investigator.
3. Serious adverse events.
4. Protocol variance (e.g. non-compliance).

K. Data Analysis

All randomized subjects who receive treatment will be included in the analysis based on intent-to-treat, defined as randomized subjects who have at least one follow up rating. Ineligible subjects who are inappropriately randomized will be excluded from the analysis. Eligibility will be reviewed by the independent adjudication committee (chaired by [name]) blind to assigned treatment and response.

For the analyses the treatment variables will remain coded and the analysts and investigators will remain blinded to variable identity during analysis and interpretation.

The change from baseline to Week 8 (or termination) in the MADRS is the primary endpoint. In order to preserve comparability with previous depression treatments studies, a similar method of analysis will be used. Missing data will be imputed using last observation carried forward (LOCF). An ANOVA on the change scores will be conducted using preplanned pairwise contrasts.

The secondary outcomes will also be analyzed using a similar ANOVA analysis, when appropriate. Categorical data (such as proportions of the sample with adverse events) will be analyzed using binary logistic regression with preplanned pairwise contrasts, chi-square tests and Fisher's exact test where cell sizes warrant.

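### Section K removes patients later ruled ineligible from the analysis without limiting this to efficacy, so read directly it also removes treated patients from the adverse-event comparison

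*Protocol*

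**What the plan says.** Section K (Data Analysis) defines one analysis set: randomised, treated subjects with at least one follow-up rating, described as intent-to-treat. It then states: "Ineligible subjects who are inappropriately randomized will be excluded from the analysis". An independent committee, blind to assigned treatment and response, reviews eligibility.

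Later in the same section: "Categorical data (such as proportions of the sample with adverse events) will be analyzed using binary logistic regression with preplanned pairwise contrasts". No separate population is named for that analysis, and no sentence elsewhere in the protocol brings treated but ineligible patients back into it.

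The adverse-event comparison is a planned analysis. The secondary objectives in Section A cover effects on "clinical response and remission rates, adverse events, quality of life, work productivity, and health services utilization". Section B adds: "Safety and adverse events data will also be systematically recorded and compared across conditions".

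**The concern.** Whether a patient was exposed to a treatment, and whether harm followed, does not depend on whether the patient met the entry criteria. Removing ineligible patients after blind review can be defended for efficacy. That defence does not carry over to harms, where the comparison should cover everyone who received treatment.

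The risk carried by the removed patients is unknown. Some exclusion criteria in Section D exist for safety: "neurologic and hematologic disease that is not stabilized, or a past history of convulsions" and "Any retinal disease or systemic illness with active retinal involvement (e.g. diabetes) that precludes the use of bright light". Patients who slipped past these could be the ones whose harms matter most. Other criteria, such as "Previous use of fluoxetine or light therapy", have no obvious link to higher risk.

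The committee is blind to arm and response, but blindness to adverse events is not stated. An event could itself bring the ineligibility to light; for example, a seizure on study might reveal a history of convulsions. This is an inference, not something the protocol describes. In that case the rule would remove the patient and the event together.

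At stake is the coverage of a stated secondary objective, mainly for rare or serious events, where one removed patient can turn one event in an arm into none.

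**Working it through.** **The text.** Four statements decide the reading.

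1. Section K gives one population definition.
2. The exclusion follows it directly and refers to the analysis without qualification.
3. The adverse-event tests sit in the same section and refer only to the sample.
4. No other section defines a population for harms.

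The most direct reading is that the exclusion applies to the adverse-event tests too.

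**The follow-up-rating condition adds very little.** Section C describes the Adverse Events Scale thus: "this self-rated scale assesses both frequency and severity of 32 adverse events". The Appendix schedules it at the same visits as the MADRS, including the termination visit. A patient with no later rating would usually have no later scale either. Only spontaneous web-CRF reports from such patients would be lost. The eligibility exclusion is therefore what matters.

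**Size: inputs.** The only document figure is 54 randomised per arm (Section D, Sample Size). The protocol gives no expected number of ineligible randomised patients, so all other counts are assumptions: k = 1, 2 or 3 treated patients per arm ruled ineligible, with risk r times that of the others (r = 1 or 3).

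**Rare event.** Suppose an arm has exactly one event. The probability that it falls in an excluded patient is

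P = r·k / (r·k + 54 − k)

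| k | r = 1 | r = 3 |
|---|---|---|
| 1 | 1/54 = 1.9% | 3/56 = 5.4% |
| 2 | 2/54 = 3.7% | 6/58 = 10.3% |
| 3 | 3/54 = 5.6% | 9/60 = 15.0% |

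When this happens with k = 1, a true 1/54 = 1.9% (Clopper-Pearson 95% CI 0.0 to 9.9%) is reported as 0/53 = 0% (0 to 6.7%).

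**Common event.** Suppose k patients are excluded in each of two arms, with 8 against 5 events among those kept. The reported risk difference is 3/(54 − k). The difference among all treated lies between (3 − k)/54 and (3 + k)/54.

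| k | Reported (points) | Possible range, all treated (points) |
|---|---|---|
| 1 | 3/53 = 5.7 | 2/54 to 4/54 = 3.7 to 7.4 |
| 2 | 3/52 = 5.8 | 1/54 to 5/54 = 1.9 to 9.3 |
| 3 | 3/51 = 5.9 | 0/54 to 6/54 = 0.0 to 11.1 |

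The limits require every excluded patient in one arm to have the event and none in the other. If the excluded patients have the same risk as those kept, the expected all-treated difference is also 3/(54 − k), and the error is zero.

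**The case against.** **The sentence may concern efficacy only.** The paragraph speaks of intent-to-treat, follow-up ratings and response, all efficacy terms. The adverse-event sentence comes later and refers to the sample, which is not tied to the intent-to-treat set. This reading is possible and cannot be ruled out. However, nothing in the wording restricts the exclusion, and Section K has no other population paragraph.

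**A safety population belongs in the analysis plan.** The absence of one from the protocol would not be a fault. The difficulty here is a rule that the protocol does state, without restriction. An analysis plan that kept these patients for harms would depart from the direct reading of that rule.

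**Safeguards exist.** Under Section F, adverse events are reported promptly on the web-CRF, and serious ones immediately by telephone. Under Section H, the monitoring committee sees all reports and can use the randomisation codes. This stands: events would not go unnoticed. It does not set the denominator of the between-arm comparison.

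**The effect is small and its direction unknown.** This also stands. Review is blind to arm, so unequal removal is not expected by design. In the common-event example with k = 1 (8/53 against 5/53), the Wald 95% interval is about ±12.4 points around 5.7, so even the extreme range for k = 3 lies within sampling error. A harsher illustration starts from 8/54 against 2/54 (Fisher p = 0.093) and removes 1, 2 or 3 patients with events from the first arm only. The p-values become 0.093, 0.157 and 0.261, none crossing 0.05. These arguments limit the severity but give no reason to keep the wording.

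**Conclusion.** The concern holds as a minor point, with medium confidence because an efficacy-only intent remains possible. Read directly, Section K removes treated patients from the planned adverse-event comparison once they are ruled ineligible.

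For common events no error is expected unless the excluded patients differ in risk. The main consequence is the possible loss of a rare or serious event from the reported comparison. The probabilities shown for that rest on the assumed 1 to 3 exclusions per arm and the assumed relative risk of 1 or 3; the protocol supports neither figure. Safety monitoring during the trial is not affected.

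**What to change.** Add one sentence to Section K, for example:

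*The eligibility and follow-up-rating exclusions apply to efficacy analyses only; adverse events will be compared in all randomised patients who took at least one capsule or used the device at least once, with Adverse Events Scale items reported among patients who completed the scale and spontaneously reported events tabulated separately.*

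If efficacy-only was always intended, this makes it explicit; if not, it corrects the rule. No new data are needed: event reports, scale scores, capsule counts and device records are already collected. The small drawback is that patients without a completed scale contribute spontaneous reports only.

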A secondary confirmatory analysis will also be conducted using a mixed-effects model with repeated measures (MMRM), under the missing at random framework (Gueorguieva and Krystal, 2004). The baseline MADRS score will be used as a covariate under this model. This model will include treatment condition and visit factors as class fixed effects and subject as random effect as well as two interaction terms between treatment condition by visit and covariate by visit, and subject as random. The treatment condition factor will have 4 levels (two monotherapies, one placebo condition, and one combination condition) and the visit factor will have 4 levels (each of the 4 treatment visits). This model using all available post-baseline evaluation in Phase II will provide the baseline adjusted least-squares means (LS-means) estimates at Week 8 by treatment condition, as well as the differences of these estimates versus placebo conditions, with their corresponding standard errors, degrees of freedom, t-test statistics and associated 95% confidence intervals. The t-test statistic at Week 8 will be used to determine the statistical significance of the primary efficacy comparisons of active versus placebo conditions.

L. Informed Consent and Ethical Considerations

The investigator will prepare a written Informed Consent Document (ICD). The subject will read the ICD and the investigator will answer any questions he/she may have. The subject must indicate willingness to participate in the study by signing the ICD. The document must also be signed by a witness and an investigator. A copy of the signed ICD will be submitted to the Study Coordinator.

This study will be conducted according to guidelines established by Good Clinical Practice (Food and Drug Administration, www.fda.gov/oc/gcp/regulations.html). The Institutional Review Boards (IRBs, or research ethics committees) of each participating site must approve the protocol and ICD. Each investigator will provide the Study Coordinator with evidence that their IRB has approved the study before subjects are entered at that site.

M. Publications and Communications

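### Section K ties the primary MADRS endpoint to an ANOVA on LOCF change scores, yet lets the MMRM it calls secondary decide significance of the primary comparisons

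*Protocol*

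**What the plan says.** Section K (Data Analysis) defines the endpoint: "The change from baseline to Week 8 (or termination) in the MADRS is the primary endpoint". It gives a reason for the method that follows, "In order to preserve comparability with previous depression treatments studies, a similar method of analysis will be used", and then the method itself: "Missing data will be imputed using last observation carried forward (LOCF). An ANOVA on the change scores will be conducted using preplanned pairwise contrasts". No other analysis is mentioned in that paragraph, so a reader takes the ANOVA on LOCF change scores to be the primary analysis.

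The MMRM paragraph of the same section opens: "A secondary confirmatory analysis will also be conducted using a mixed-effects model with repeated measures (MMRM), under the missing at random framework". It specifies baseline MADRS as a covariate, treatment and visit effects with interactions, and least-squares means at Week 8. It closes: "The t-test statistic at Week 8 will be used to determine the statistical significance of the primary efficacy comparisons of active versus placebo conditions".

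The Sample Size part of Section D sets a two-sided Bonferroni-corrected alpha of 0.017 for each of three comparisons with placebo, and allows for 20% dropout. It does not say which analysis that alpha belongs to.

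**The concern.** The MMRM paragraph ranks its analysis second in its first sentence and gives it the primary decision in its last. The paragraph before it has already attached a different analysis to the primary endpoint. Nothing says what is concluded if one analysis is significant and the other is not.

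The headline conclusion is at stake. If the results differ, either could be reported as primary with a sentence of the protocol to support it. The three comparisons at 0.017 already use the whole 5% error allowance, so there is no room for a second route to significance. Even if the choice were made in good faith, a critic could point to the other sentence.

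**Working it through.** **1. The two analyses side by side (Section K).**

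| Feature | ANOVA paragraph | MMRM paragraph |
|---|---|---|
| Stated role | Follows directly from the primary endpoint | Called secondary, then decides the primary comparisons |
| Missing data | LOCF | Missing at random |
| Baseline MADRS | No covariate named | Covariate, with a by-visit interaction |
| Target | Last available value (Week 8 or termination) | Week 8 |

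If the ANOVA decides, the closing MMRM sentence is wrong as written. If the MMRM decides, the secondary label is wrong and the ANOVA has no decision role. Both readings require a change of text.

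**2. The plan's own figure.** Inputs from Section D: difference 3.5, power 80%, alpha 0.017 (0.05/3 = 0.0167), 54 per arm, 20% dropout. The SD of MADRS change is not stated, so 54 cannot be reproduced independently; only the implied SD can be found.

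- n = 2 × (2.387 + 0.842)² × SD² / 3.5²
- Completers: 54 × 0.8 = 43.2, so 43 per arm
- Implied SD = 3.5 / (3.228 × √(2/43)) = 5.03
- Check with SD 5: n = 42.5, rounded up to 43; 43/0.8 = 53.75, rounded up to 54

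The figure is coherent if the SD is about 5. It does not show which analysis was meant.

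**3. Error if either analysis may count (illustration).** Assume two bivariate normal statistics with correlation ρ, each tested at |Z| > 2.387. The values of ρ are assumptions. The family-wise figures are simulated for three comparisons sharing the placebo arm.

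| ρ | Per-comparison error, either | Family-wise error, either | Verdicts differ at 50% power | Verdicts differ at 80% power |
|---|---|---|---|---|
| 0.80 | 0.028 | 7.3% | 20% | 14% |
| 0.90 | 0.025 | 6.5% | 14% | 10% |
| 0.95 | 0.023 | 6.0% | 10% | 7% |

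With one named analysis the per-comparison error is 0.017 and the family-wise error about 4.5%.

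**4. Can the two analyses really part company? (illustration)** The simulation had 54 per arm and ratings at Weeks 0, 1, 2, 4, 6 and 8. It assumed an SD rising from 4.5 to 9 and dropout that is missing at random. A sequential regression adjusted for baseline stood in for the MMRM.

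- No effect, about 19% dropout in both arms: the two estimates correlate at 0.91. The error per comparison is about 1.8% for one analysis and 2.6% for either.
- True difference 3.5, dropout 19% and 18%: LOCF averages 3.15 and the model 3.49. Verdicts differ in about 16% of trials.
- True difference 3.5, dropout 19% and 34%: LOCF averages 1.92 and the model 3.52. Verdicts differ in about 33%.
- No effect, dropout 19% and 36%: LOCF shows a spurious 0.9 points and the model about 0.

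The model does well here partly because the simulated dropout satisfies its assumption.

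**5. Is the MMRM ready to be primary?** Section K gives its visit factor 4 levels, one per treatment visit. The Appendix schedules the telephone MADRS after baseline at Weeks 1, 2, 4, 6 and 8, which is five. Section F agrees: two visits at one-week intervals, then three at two-week intervals. The endpoint wording in Section K allows termination in place of Week 8, and Section B describes change from baseline to termination. Neither matches a Week 8 contrast.

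**The case against.** The strongest reply is that a hierarchy exists. The ANOVA follows the primary endpoint, the MMRM is labelled secondary, and the closing sentence merely says which MMRM statistic counts (Week 8, not another visit or the interaction) when that model addresses the primary comparisons. This reading is possible, and it limits the fault to one sentence. But the sentence says the test determines significance, not that it supports a result obtained elsewhere, so the text does not force that reading.

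A statistical analysis plan, not shown here, might settle the matter. It would still have to override one of two protocol statements.

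Section K also keeps analysts and investigators blind to treatment codes during analysis and interpretation. That limits directed selection between the two results but does not say which one decides.

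On LOCF the reply largely stands. LOCF is stated openly, with a reason, and a missing-at-random analysis accompanies it. A reader might infer that the LOCF result will be biased in a known direction. The protocol gives only one overall dropout figure, with no rates, timing or reasons by arm, so neither direction nor size can be known in advance.

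A reader might also infer a serious loss of power. Suppose the 20% who drop out show a 1-point difference; the contrast becomes 0.8 × 3.5 + 0.2 × 1 = 3.0. Power of about 65% then follows only if 43 per arm are analysed. LOCF keeps every treated patient with at least one follow-up rating, so up to 54 per arm. At SD 5.03, power is Φ(3.0 / (5.03 × √(2/54)) − 2.387), or about 76%. The 65% figure is not supported.

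**Conclusion.** The contradiction stands on the text alone and should be resolved before unblinding, because it decides what the trial may conclude. Its numerical consequence is not fixed by the protocol. The rise from 0.017 to about 0.023 to 0.028 per comparison assumes correlations of 0.95 to 0.80 and that whichever result is significant gets reported. It measures what the ambiguity would permit and does not show that the sponsor intends it. The simulated disagreement rates and LOCF shifts likewise rest on assumed SDs, response curves and dropout patterns.

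LOCF is a subordinate point. With about 20% dropout, and values that may be carried forward from as early as Week 1, it can bias the contrast if dropout rate or timing differs between arms. That is a reason to prefer the MMRM as the single primary analysis; it is not a second contradiction.

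**What to change.** Name one analysis as primary for the three placebo comparisons at alpha 0.017, label the other a sensitivity analysis, and reword both paragraphs of Section K so that only the named one determines significance.

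The baseline-adjusted MMRM contrast at Week 8 is the better candidate. Keeping the ANOVA with LOCF as a sensitivity analysis preserves the comparability that the protocol gives as its reason. If the MMRM is chosen:

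- remove its secondary label;
- change the visit factor from 4 to 5 levels (Weeks 1, 2, 4, 6 and 8);
- align the endpoint wording in Sections B and K with the Week 8 target.

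If the sponsor keeps the ANOVA as primary, the closing MMRM sentence must lose its decision role.

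The cost is a few wording changes in two sections and, with the MMRM, slightly less direct comparability with older LOCF trials. Both analyses are already planned, and the sample size and alpha stay as stated.
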